11. ETHICAL AND REGULATORY ASPECTS

The clinical trial must be conducted in accordance with:

- the ethical principles of the current version of the Declaration of Helsinki,

- the guideline for Good Clinical Practice of the International Conference on Harmonization (ICH–E6, 07/17/96),

- European Directive 2001/20/EC on the conduct of clinical trials,

- the French Huriet Act (No. 88-1138) dated December 20, 1988 concerning the protection of clinical trial subjects, amended by the French public health law No. 2004-806 dated August 09, 2004,

- the French data protection and civil liberties law No. 78-17 dated January 06, 1978, amended by law 2004-801 of August 06, 2004 regarding the processing of personal data,

- French law No. 2004-800 dated August 06, 2004 concerning bioethics.

Research Ethics Board

Before conducting biomedical research on human subjects, the sponsor is obliged to submit the project to one of the REBs with jurisdiction where the coordinating investigator practices, for its opinion.

The sponsor also submits applications for substantial amendments to the initial project to the REB for its opinion.

Competent Authority

Before conducting a clinical trial or having one conducted, the sponsor of the trial shall apply to the ANSM for authorization.

Subject information and consent

Before biomedical research is conducted on a person, their voluntary, written, informed consent must be obtained, after they have been fully informed by the investigator during a consultation and given enough time to consider their decision.

Information intended for trial subjects must include all of the particulars set out in the French public health law of August 09, 2004 and must be written in straightforward language that the patient can understand.

The consent form must be signed and dated personally by the trial subject and the investigator (the original copy shall be archived by the investigator, and one copy will be given to the trial subject).

The patient information leaflet and informed consent form must be combined into a single document to ensure that all of the information is given to the trial subject.

Responsibilities of the sponsor

The sponsor of the clinical trial is the individual or legal entity that takes the initiative for the biomedical research on human subjects, manages the trial, and ensures that provision has been made for its funding.

The sponsor must be established in the European Community or, failing that, have a legal representative in a member state.

The sponsor's main responsibilities are to:

- take out civil liability insurance,
- request the opinion of the REB on the initial project and substantial amendments,
- request authorization for the initial project and substantial amendments from the competent authority,
- provide information about the trial to the site directors, investigators, and pharmacists,

- report any suspected unexpected serious adverse events related to any of the trial treatments to the competent authority, ANSM and EMEA (European pharmacovigilance database, Eudravigilance), and send this information to the REB and the trial investigators,

- submit the annual safety report to the competent authority and the REB,
- notify the competent authority of the start and end of the trial,
- write the final clinical study report,
- send the trial results to the competent authority, REB, and trial subjects,

- archive essential trial documents in the sponsor's folder for a minimum of 15 years after the trial has ended.

Responsibilities of investigators

The principal investigator of each establishment concerned undertakes to conduct the clinical trial in accordance with the protocol approved by the REB and the competent authority.

The investigator must not make any changes to the protocol without the written authorization of the sponsor and unless the REB and the competent authority have approved the proposed changes.

It is the responsibility of the principal investigator to:

- provide the sponsor with his/her curriculum vitae as well as those of his/her co-investigators,

- identify the members of his/her team who are participating in the trial and define their responsibilities,

- recruit patients once authorized to do so by the sponsor.

It is the responsibility of each investigator to:

- obtain informed consent, personally signed and dated by the subject, before carrying out any trial-specific screening procedures,

- regularly complete the case report form (CRF) of each patient enrolled in the trial and allow the clinical research assistant (CRA) appointed by the sponsor to have direct access to source documents, so that the latter can validate the data on the CRF,

- date, correct, and sign corrections on the CRF of each patient enrolled in the trial,

- accept regular visits by the monitor, and any auditors appointed by the sponsor or inspectors from the regulatory authorities.

All of the trial-related documentation (the protocol, consent forms, case report forms, investigator brochure, etc.) and source documents (laboratory results, X-rays, consultation reports, physical exam reports, etc.) are considered confidential and must be kept in a safe place. The principal investigator must store the data and a patient identification list for a minimum of 15 years after the end of the study.

12. Data Safety Monitoring Board (DSMB)

The DSMB will be set up to safeguard patients, to make sure that the trial is conducted ethically, to evaluate the trial's risk-benefit balance, and to independently review the scientific results during or at the end of the trial. The committee's role is to advise the sponsor, but the final decision on implementing the DSMB proposed recommendations rests with the sponsor.

13. Quality assurance

In order to guarantee the authenticity and credibility of the data in accordance with Good Clinical Practice (GCP), the sponsor shall put in place a quality assurance system which includes:

- Management of the trial in accordance with GFM's procedures,

- Quality control of the investigator site data by the monitor, whose role is to check the data in the case report form for concordance and consistency with the source documents,

- The possible audit of investigator sites.

14. Ownership of the data and confidentiality Central

The investigator undertakes that he/she and anyone who monitors the conduct of the trial will ensure the confidentiality of all of the information provided by GFM until the trial results are published. This confidentiality requirement shall not apply to information that the investigator gives to patients in connection with their participation in the trial or to previously published information.

The investigator undertakes not to publish, disclose, or use any trial-related scientific or technical information, in any way, either directly or indirectly.

Nevertheless, in accordance with Article R 5121-13 of the French public health code, the site and the investigator can give information about the trial:

- to the minister for health,
- to public health inspectors (medical doctors or pharmacists),
- to the Competent Authorities.

No written or verbal comments can be made about the trial without the sponsor's consent, since all of the information provided or obtained while the trial is being conducted legally belongs to the sponsor, which can use the information at its own discretion.

15. Publication policy

All of the information arising from this trial shall be considered confidential, at least until completion of the appropriate analysis and subsequent checks by the trial sponsor, coordinating investigator, and statistician.

Any publications, abstracts or presentations that include results from the trial must be submitted to the sponsor for approval.

Any communications, articles, or presentations must also include a section mentioning the GFM and the organizations that supported the research financially.

The trial's coordinating investigator will be the main (first or last) author.

The first or last author (depending on the position given to the coordinating investigator) will be jointly selected by the sponsor and the CI.

The following investigators will be cited in order of the number of patients recruited for multicenter trials, or based on their involvement in the protocol and/or the disease. The trial statistician will also be cited.

Similarly, publications of ancillary results (biological studies) shall include the name of the person who carried out the ancillary study, as well as the names of anyone else involved in the ancillary study.

16. Insurance

In accordance with current legislation, insurance has been taken to cover any physical harm or other incapacity that may result from administration of the investigational treatment, in accordance with the study protocol.

18. APPENDIX

Appendix 1. Performance status assessed by ECOG

G R A D E	ECOG
0	Fully active, able to carry on all pre-disease performance without restriction
1	Restricted in physically strenuous activity but ambulatory and able to carry out work of a light or sedentary nature, e.g., light house work, office work
2	Ambulatory and capable of all selfcare but unable to carry out any work activities. Up and about more than 50% of waking hours
3	Capable of only limited selfcare, confined to bed or chair more than 50% of waking hours
4	Completely disabled. Cannot carry on any selfcare. Totally confined to bed or chair
5	Dead

* As published in Am. J. Clin. Oncol.:

Appendix 2. New York Heart Association (NYHA) Functional Classification

NYHA Class	Symptoms
I	No symptoms and no limitation in ordinary physical activity. E.g., shortness of breath when walking, stair climbing, etc.
П	Mild symptoms (mild shortness of breath and/or angina pain) and slight limitation during ordinary activity.
Ш	Marked limitation in activity due to symptoms, even during less-than-ordinary activity (e.g. walking short distances, ~ >20 - 100m). Comfortable only at rest.
IV	Severe limitations. Experiences symptoms even while at rest, mostly bed bound patients

Appendix 3. SORROR SCORE

Comorbidity	Definition	Score
Arrhytmia	Atrial fibrillation or flutter, sick sinus syndrome, or ventricular arrhythmias	1
Cardiac	Coronary artery disease [*] , congestive heart failure, myocardial infarction, or EF \leq 50%	1
Inflammatory bowel disease	Crohn disease or ulcerative colitis	1
Diabetes	Requiring treatment with insulin or oral hypoglycemics but not diet alone	1
Cerebrovascular disease	Transient ischemic attack or cerebrovascular accident	1
Psychiatric disturbance	Depression or anxiety requiring psychiatric consult or treatment	1
Hepatic, mild	Chronic hepatitis, bilirubin > ULN to 1.5 x ULN, or AST/ALT > ULN to 2.5 x ULN	1
Obesity	Patients with a body mass index > 35 kg/m ²	1
Infection	Requiring continuation of antimicrobial treatment after day 0	1
Rhumatologic	SLE, RA, polymyositis, mixed CTD, or polymyalgia rheumatica	2
Peptic ulcer	Requiring treatment	2
Moderate or severe renal	Serum creatinine > 205 μ mol/L, on dialysis, or prior renal transplantation	2
Moderate pulmonary	DLco and/or FEV1 66%-80% or dyspnea on slight activity	2
Prior solid tumour	Treated at any time point in the patient's past history, excluding nonmelanoma skin cancer	3
Heart valve disease	Except mitral valve prolapsed	3
Severe pulmonary	DLco and/or FEV1 < 65% or dyspnea at rest or requiring oxygen	3
Moderate/severe hepatic	Liver cirrhosis, bilirubin > 1.5 x ULN, or AST/ALT > 2.5 x ULN	3

*One or more vessel-coronary artery stenosis requiring medical treatment, stent, or bypass graft.

EF indicates ejection fraction; ULN, upper limit of normal; SLE, systemic lupus erythmatosis; RA, rheumatoid arthritis; CTD, connective tissue disease; DLco, diffusion capacity of carbon monoxide.

Appendix 4. Serious infectious disease

Infections which should be considered:

- -pneumonia
- -severe sepsis defined in Appendix 5
- -symptomatic bacteriemia
- -arthritis / osteomyelitis
- -pyelonephritis or prostatis
- -profound abscess
- -meningitis or encephalitis
- -invasive aspergillosis
- -candidemia
- -CMV disease
- -adenoviral disease
- -disseminated viral infections (involving at least 2 organs)
- -skin or subcutaneous infections

Data concerning benign or asymptomatic infections will not be collected for the protocol:

- -superficial fungal infection (skin, mucous) -upper respiratory tract infection
- -sinusitis
- -cystitis
- -viral infection requiring pre-emptive treatment
- -herpes simplex infection
- -VZV infections (except severe form leading to pneumonia)
- -CMV reactivation
- -EBV reactivation
- -adenoviral reactivation

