3.2 Secondary Objectives

- ✓ Comparison between patients with or without a donor for:
 - a. Cumulative incidence of complete response at 36 months
 - b. Cumulative incidence of Transformation in AML at 36 months (according to WHO criteria, > 20% blasts in peripheral blood or bone marrow)

Evaluate:

- ✓ Risk factors for outcome (remission, mortality)
- Risk factors for overall survival (age, disease characteristics...) including iron overload (ferritin, plasmatic iron markers, MRI)
- ✓ The efficiency of chelation will be assessed at 3 months after inclusion for all patients
- ✓ Feasibility of the transplant define by the proportion of patients with a donor who undergo the transplantation (expected between 80 and 95%)
- ✓ Proportion of patients with iron overload (Serum Ferritin (SF) > 1000 ng/mL or RBC transfusion > 20) at time of inclusion and at 16 months after inclusion for non-transplanted patients and 12 months post-transplant for transplanted patients
- ✓ The effect of chelation post-transplant will be measured by SF level: SF < 1000 ng/mL, SF > 1000 ng/mL, SF > 1500 ng/mL and also by percentage of patients with SF decrease of at least 30%
- Eligibility of post-transplant Exjade[®] treatment defined by the proportion of patients with iron overload who can benefit from Exjade[®] after the transplantation (% of patients without contraindication to Exjade[®] 3 months after transplant) and who can maintained it at least 6 months or until SF < 700 ng/mL
- ✓ Assessment of change of Ferritin level (% of decrease) and MRI at 12 months post-transplant
- Evolution of innovative iron markers including Non-transferrin binding iron (NTBI), labile plasmatic Iron (LPI) and Hepcidine at time of inclusion (before Exjade®), at 3 months (patients potentially treated by Exjade®) and 16 months post-inclusion for all patients; in transplanted patients these markers will be measured just before conditioning regimen (J-5), just before the transplantation (J0), at D7, 30, 100 and 12 months after transplant. All these markers will be tested as risk factors for outcome (survival, non-relapse mortality and progressive disease)
- ✓ Quality of Life study (EORTC questionnaire at registration, 12, 24 and 36 months)
- ✓ Grade III or IV toxicity (hematological and non-hematological) recorded according to NCI CTC criteria version 4.0
- ✓ Cumulative incidence of severe infection at 12 months

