4.1. Inclusion criteria

1/ Signed Informed consent

2/ Patients should be intermediate 1 or low according to IPSS with at least one poor prognosis feature

- MDS classified according to revised IPSS at least intermediate
- □ RBC transfusion dependent anemia and failure to 2 lines of therapy if eligible (including EPO, Lenalidomide or demethylating agents ...) with the exception of pure RARS with isolated SF3B1 mutation
- thrombocytopenia < 20 G/L requiring transfusion

- □ neutropenia < 0.5 G/L associated with severe infection (defined as requiring hospitalization)
- 5q- and lenalidomid failure especially but not only with TP53 mutated

$3/ \text{Age} \ge 18 \text{ and} < 70 \text{ years}$

For young patients, 18-45 years, Fanconi disease and dyskeratosis should be ruled out by standard test in order to test frequent constitutional genetic alteration.

4/ Patient for whom a transplantation from a matched donor, (8/8 (HLA A, B, C, DRB1) identical at molecular level) unrelated donor or matched sibling), is considered irrespective of donor availability

5/ Performance status 0-2 on the Eastern Cooperative Oncology Group (ECOG) Scale (at time of screening)

6/ Negative pregnancy and adequate contraception (including in male patients wishing to father), if relevant

7/ Wash-out of at least 30 days since a previous treatment with Vidaza[®], Lenalidomide, EPO or any other treatment inducing cytopenias

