8.2. Visits

For all enrolled patients, visits will be performed:

- at inclusion
- every two weeks during the first 4 weeks (first month)
- every 4 weeks from the 5th week to the 26th week (until 6th month)
- every 8 weeks from the 27th week to the 52th week (until 12th month)
- every 12 weeks from the 53th week to the end of study.

At each patient visit, the following information will be registered:

- Grade III to IV adverse events (classified according to NCI- CTCAE 4.0) http://evs.nci.nih.gov/ftp1/CTCAE/CTCAE_4.03_2010-06-14_QuickReference_5x7.pdf

- Treatment by Exjade[®] and its dose
- Clinical assessment (every 2 weeks on first month)
- Weight, PS, serious infectious disease (defined in Appendix 4)
- Transfusion history (platelet and RBC) including the research of allo-immunisation (RAI)
- AST, ALT, serum bilirubin, serum creatinine, PAL, LDH, GGT, CRP

- Proteinuria (rapid urine test)

- Pregnancy test, if applicable
- Blood cell count including reticulocytes (every week during the 1th month then every 4 weeks)
- Ferritin level, transferrin level and saturation, plasmatic iron level
- In case of disease progression/relapse suspicion, marrow + cytogenetic analysis

Specific information for specific point (after inclusion):

- Quality of life questionnaire (EORTC) at 12, 24 and 36 months

- Centralized biological study (hepcidine, LPI, NTBI): At 3 and 16 months after inclusion (specific form in Appendix 10)

- **Bone marrow aspiration** with cytogenetic (local laboratories) and molecular biology (CHRU Lille) will be performed according to local policy but at least once a year

For patients who received a transplant:

- Pre-graft tests including cardiac assessment and respiratory assessment with pulmonary tests

- **Centralized biological study (hepcidine, LPI, NTBI):** just before conditioning regimen (D-5), just before transplant on day 0, and on day 7, 30, 100, 365 post-transplant

- Between 2 to 3 months after the transplant, a **bone marrow aspiration** (with shipment for biological study: BM 2 ml EDTA)

- At least one post-transplant **chimerism** in blood after engraftment on day 30. The chimerism will be repeated only if the first one is not donor > 95% or in cases a rejection is suspected

- Acute GVHD grade per organ at each visit (Appendix 6)

- Neutrophil engraftment and platelet engraftment (within 60 days post-transplant)

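### Appendix 4 puts VZV encephalitis and disseminated VZV without pneumonia on both its lists, and the severe-infection endpoint in 3.2 does not name Appendix 4 as its definition

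*Protocol*

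**What the plan says.** Section 3.2 of the protocol lists as a secondary item "Cumulative incidence of severe infection at 12 months". It gives no definition there and does not point to an appendix.

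Section 8.2 sets out what is registered at each visit and includes "Weight, PS, serious infectious disease (defined in Appendix 4". This is the only place where the protocol attaches a definition to infection data collected during follow-up.

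Appendix 4 then gives two lists.
- To be considered: among others, pneumonia, "meningitis or encephalitis" and "disseminated viral infections (involving at least 2 organs". None of these three is restricted by pathogen.
- Not to be collected: this list opens with "Data concerning benign or asymptomatic infections will not be collected for the protocol". It contains herpes simplex infection, with no exception, and "VZV infections (except severe form leading to pneumonia".

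The words severe infection are defined elsewhere only inside an eligibility criterion, in 4.1 and the synopsis: "neutropenia < 0.5 G/L associated with severe infection (defined as requiring hospitalization".

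**The concern.** A site that sees VZV encephalitis, or VZV in two organs without pneumonia, finds the event on the list to record and on the list not to collect. The appendix does not say which governs. If the site follows the VZV line, a clearly severe infection never enters the item that most plausibly feeds the 12-month endpoint. The analysis cannot then fully repair this, because an SAP can choose a definition but cannot recover an infection form that sites were told not to complete.

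Section 3.2 makes the gap slightly wider. The endpoint says severe, the visit item says serious, and no cross-reference joins them. Appendix 4 is very probably the intended source, but the text leaves the reader to infer it.

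**Working it through.** The protocol states no figure on this point, so the check is a comparison of texts. Each event type is placed against the two lists in Appendix 4.

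| Event | List to record | List not collected | Result |
|---|---|---|---|
| VZV pneumonia | Yes, as pneumonia | No, named as the exception | Consistent: recorded |
| VZV encephalitis | Yes | Yes, not excepted | On both lists |
| VZV in at least 2 organs, no pneumonia | Yes | Yes, not excepted | On both lists |
| HSV encephalitis | Yes | Yes by the item, arguably no by the list's heading | Ambiguous |
| CMV or adenoviral disease | Yes | No, only reactivation is listed | Consistent: recorded |

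**Does the heading of the second list settle it?** That heading confines the list to benign or asymptomatic infections.
- For HSV it helps. The HSV line has no qualifier, so it can be read as benign HSV only, which leaves HSV encephalitis to be recorded. That reading is available but not compelled.
- For VZV it does not help. If the heading already removed severe disease, the pneumonia exception would be unnecessary. Naming one severe form as the exception implies that other severe forms remain excluded.

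**Does the appendix show how to avoid this?** Yes. For CMV and adenovirus it puts disease on one list and reactivation on the other. HSV and VZV are not divided in this way.

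**Link to the endpoint.** The chain is 3.2 (severe infection, undefined), then 8.2 (serious infectious disease, by Appendix 4), then Appendix 4 (lists in conflict for VZV). The first step is not written down.

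**Scale.** The protocol gives no rate for any infection, so the number of affected patients is unknown. Only the unit of change can be stated. With the planned 62 donor and 43 no-donor patients, one reclassified patient moves a crude 12-month proportion by 1/62 = 1.6 points or 1/43 = 2.3 points. A patient is reclassified only if no other Appendix 4 infection occurs in the window, because a cumulative incidence ordinarily counts the first event.

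**The case against.** The case against is strong on several points.

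**Two definitions of the endpoint.** A reader might infer that the endpoint has two rival definitions, hospitalization in 4.1 and the list in Appendix 4. The documents do not support this. The wording "associated with severe infection (defined as requiring hospitalization" qualifies neutropenia at entry, and nothing tells sites to apply it in follow-up. What stands is a missing cross-reference and a change of word.

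**HSV encephalitis flatly contradictory.** A reader might infer this from the item wording alone. The heading of the second list permits a consistent reading, so ambiguous is the right word.

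**Sites do count differently, mainly in transplanted patients.** The text shows only that sites could differ. No figure supports a concentration in transplanted patients, and section 6.1 specifies herpes simplex prophylaxis for them.

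**A material shift in the estimate.** One could assume an incidence and a number of reclassified patients and compare the shift with a standard error. Both inputs would be invented, so the result would be no evidence of size.

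**Other records exist.** Grade III-IV adverse events are registered at every visit (8.2), and an event that requires or prolongs hospitalization is an SAE (10.2). This mitigation is real but partial. These records are a different instrument, not coded to Appendix 4. Routine SAE reporting also ends 30 days after transplant or after the last study drug (10.3), apart from later events thought related.

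**Further details.** Time origin, first-event rule and competing event are commonly left to an SAP, which is not at hand. A severity condition for skin infections would be a preference. Neither is part of this point.

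**Conclusion.** The point holds in a narrow form. Appendix 4 contradicts itself for VZV encephalitis and for VZV in at least two organs without pneumonia, and it is unclear for HSV encephalitis. Section 3.2 does not tie its endpoint to Appendix 4, although that is the only definition attached to the infection data collected at visits.

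The impact is limited. It concerns a small set of event types in one secondary endpoint, which is not among the listed donor versus no-donor comparisons. Its size cannot be derived from the protocol. Adverse event and SAE records may recover part of what is lost. Overall survival, the primary endpoint, is unaffected.

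The conclusion assumes that Appendix 4 is the intended source of the endpoint, which 8.2 makes likely but 3.2 does not state.

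**What to change.** In Appendix 4, limit the HSV and VZV exclusions to localized, non-severe disease. Alternatively, add one sentence saying that the list to record takes precedence. Either way, encephalitis, pneumonia and disease in at least two organs should always count, whatever the virus.

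In 3.2, state that severe infection means a serious infectious disease as defined in Appendix 4. Keep the hospitalization wording in 4.1 and the synopsis for eligibility only.

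The cost is a wording change in two places and a short CRF completion note. If patients have already been followed under the present wording, the grade III-IV adverse event and SAE records can be searched for HSV and VZV events that the Appendix 4 item may have missed.
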